Abstract

Introduction

The concept of prehabilitation is well established in cancer and orthopaedic populations. However, amongst the cardiac surgery population, this concept is relatively new. Over the last 10 years, only a handful of studies were published. All the studies focused on elective cardiac surgery population. Over the last 5 years, three further registered studies have focused on the elective cardiac surgery population. This pilot study will focus on the acute inpatient cardiac surgery population. We aim to assess the feasibility and impact of multimodal prehabilitation on inpatients waiting for cardiac surgery.

Methods and analysis

In advance of the study, we will be conducting a separate audit with the local trusts permission. The purpose of the audit is to understand the population that present to our department for cardiac surgery. This will hopefully help us identify the number of patients that could benefit from the intervention, the demographics, how they present, diagnosis and the potential impact of waiting times on these patients. This audit is performed based on pre-collected data from patients who had cardiac surgery in 2022. All patients who had cardiac surgery in our department will be entered onto an audit database as routine. Information from this database is extracted for national audit purposes when required. We will be extracting the required information from this database to answer the questions outlined above. All the information will be anonymous. As this information is routinely collected by the cardiac audit department, we will be seeking local institutional approval for this.

Trials involving patients should be co-designed with them to improve the engagement and success of the program. We will be doing a survey on inpatients waiting for cardiac surgery in Castle Hill Hospital to gauge their interest. These patients will not be enrolled into the main pilot study but we will seek their opinion on the intervention and trial design based on their experience waiting for cardiac surgery. Patients will be approached in person, informed about the purpose of the survey, consented and they will be asked set questions regarding their opinion on the concept of inpatient prehabilitation, the patient information sheet, psychoeducation leaflet, and the intensity of the program. We will enquire about their interest in participating if they had the opportunity. The data collected will be anonymous.

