This single centre, prospective, pilot feasibility trial will recruit 20 inpatients awaiting cardiac surgery. Measurements will be taken at the start of the trial, 7 days after intervention, and 14 days after the intervention or before the day of surgery. The primary outcome measure will be feasibility and practicality of the programme in acute inpatient population. We will be looking into participant eligibility, acceptability, recruitment rates, completion rates and barriers to implementing a prehabilitation programme. Secondary outcomes include safety (incidence of adverse events directly related to the study), improvement in 6 minutes walk test (6MWT), hand grip strength, quality of life, anxiety scores and spirometry. At the end of the trial, we will be seeking the feedback of the participants to help us improve the design further.

Ethics and dissemination

Trial Registration number

Introduction

According to the National Adult Cardiac Surgery Audit (NACSA) over 30,000 heart surgeries are performed every year in the UK.¹ With the increased life expectancy in the UK, the number of heart surgeries is unlikely to reduce. Advancing age is often associated with frailty; a physiological state of diminished response to stressors due to decreased reserve secondary to multiple comorbidities and homeostatic dysregulation.² Accordingly, it is unsurprising that frail patients have poorer outcomes following an illness and incur a higher healthcare cost. There is evidence that frailty is a reversible condition with an improvement of diet, and exercise.³ A randomised control trial found a combination of resistance training and nutritional supplement led to not only an increase in muscle bulk and strength but also improved mobility.³ The possibility of reversing or slowing down this medical condition has led to a lot of interest in the subject.

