This trial will be conducted in Castle Hill Hospital (CHH) which is part of Hull University Teaching Hospital NHS Trust, a tertiary hospital in United Kingdom. Assessments will be conducted on the cardiac surgery and cardiology ward. Ahead of the pilot study, we will be conducting an audit looking into patients who had cardiac surgery in 2022. This information will be obtained from an existing audit database in the department. All patients who had cardiac surgery in our hospital

IRAS ID 330859

Version Number: 3

Date: 06/11/2023

have information relating to their admission collected as a routine. This is done for audit, clinical assurance and service evaluation purposes. We will be requesting the relevant information for our analysis. All patient information will be anonymous. The purpose of this audit is to try and build a picture of the population that present for cardiac surgery. We will be interested to know the demographic, comorbidities and how the present to the service. This audit should help us identify the number of patients that could potentially benefit from our intervention and the potential impact of preoperative waiting time on patient outcome such as post-operative complications and post-operative stay.

Patient and public involvement (PPI) is very important in ensuring the success of a study or program. Whilst our preliminary survey has indicated an interest in prehabilitation, we will be doing further interviews to refine the design of this study and of any future studies. Inpatients waiting for cardiac surgery will be approached and given information about the project. They will then be invited to participate in the survey which is done via 1:1 interview. Once they consent, we will then be providing them with details of what the prehabilitation would entail, the patient information sheet and psychoeducation leaflet. Patients will be consulted on the frequency, duration and intensity of the program. The survey will hopefully identify any potential barriers to success as well as solutions to improve engagement. Participants for the PPI will not be recruited into the pilot study.

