Potential participants for the pilot study will be identified from the cardiology team on the ward and acute admission board in the hospital. The cardiology team will give an indication that the patient is likely for surgery and any language barrier. For the purposes of this pilot, only patients that present directly to CHH and able to communicate in English will be considered. Initial screening for the patient will be done by the research team upon speaking to the cardiology team. Eligible participants will be approached by a member of the research team, provided verbal information and following that given the patient information leaflet. They will then be allowed some time to go through the information. The researcher will then return to ask if they would like to participate and consent them if they agree. Once consented, participants will be asked to perform the baseline test. Interventions will begin soon after this. Interventions will be delivered as a mix of information leaflet, face to face session and online video. Surgery and post-operative hospitalisation will take place in the same hospital.

Objective

Primary objective

The primary objective is to determine the feasibility of a prehabilitation program in acute in patient population. We will be looking at the eligibility rates, enrolment/ recruitment rates, practicality of a prehabilitation program in terms of logistical challenges to developing and implementing the program (deliverability), uptake rates, acceptability and completion rates of an inpatient prehabilitation program.

Secondary objective

Secondary objectives are to identify any changes in 6-MWT, hand grip strength, quality of life, spirometry and mental health before and after the program. We will be collecting information on adverse events, length of stay, complication(s) and readmission during this study. This will give us signals for safety concerns and potential efficacy of the program.

Eligibility criteria

Inclusion criteria

All patients over the age of 18 scheduled for acute cardiac surgery will be given consideration to participate in this clinical trial.

Exclusion criteria

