We will be sending out questionnaires pertaining to the patient's mental health. Patient's that score highly or show any features of mental health problem that could impact their safety will either be asked to self refer for help or be contacted by a clinical psychologist. The intervention offered will depend on the severity of condition.

Outcome measures

The primary outcome is the feasibility and acceptability of the multimodal program. Feedback will be obtained from the patient regarding the acceptability, achievability and general interest in the program.

Feasibility will be assessed by determining the number of eligible patients, participants recruited, participated and retained at the end of the intervention, the proportion of intervention sessions delivered and fidelity of delivery. Moreover, participant recruitment, retention and adherence to the intervention will be measured, as well as any adverse events.

To determine the acceptability of the intervention and to explore barriers and enablers to the implementation of the intervention, interviews will be conducted amongst participants, and staff involved in referral and intervention delivery.

Secondary objectives:

- To identify a signal of efficacy for positive changes in physical health exercise, mental wellbeing, and quality of life (using tools described);
- To identify differences in length of hospital stay, complications and readmission rates to hospital following surgery compared to usual care (based on previously collected data);
- Indications of safety concerns with prehabilitation in acute inpatient population. This is based on reported adverse events

The 6 minute walk test, hand grip, quality of life measure, spirometry and cardiac anxiety score will be measured at three points, before the intervention, day 7 and day 14 or before the surgery. If the surgery happens before day 7, there will only be two measurements. Information on any cardiac symptoms and their association with the exercise will be documented.

The end of the trial is defined as the day of surgery for the last participant. Participants may choose to withdraw at any point of the trial. If they are changes in circumstances which would impact their ability to complete the trial, they will be withdrawn by the clinician.

Statistical method

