Data will be analysed at the end of the study. We will be analysing the data for the eligibility rate, recruitment rates, number of patient that participated and completed the intervention. We will be looking at the number supervised of sessions that were successfully delivered before the surgery as well as the number of unsupervised sessions that the participants achieved. Qualitative analysis will be used to determine the acceptability of the intervention and barriers to implementation.

Data of length of stay, complication rates and readmission rates will be collected and analysed. These can be compared to national data. Improvement in 6MWT, hand grip, EQ-5D-5L and CAQ will indicate potential efficacy of intervention.

Ethics

Ethical approval has been obtained from Hull York Medical School ethics committee. We have received REC approval via IRAS.

Data management

All staff handling patient data will need to comply with hospital data protection policy. The research team will need to have evidence of up-to-date Information Governance training. Data will be used according to the General Data Protection Regulation (GDPR) regulation. Only authorised research members will be given access to the required data. Electronic information on the study will be stored on approved devices provided by the institution. Written data obtained from the study will be kept in a locked cabinet in the department. All information collected will be anonymised. Individuals will not be identified through any reports or publications that result from the trial.

Discussion

Prehabilitation is one of the recommendations of Enhance Recovery After Surgery (ERAS). Although ERAS is well practiced in other surgical population (the society has been around since 2001), ERAS-C is relatively new (established 2017). Despite this, the implementation of prehabilitation in the UK has been slow. A recent survey found that only 13% of cardiac centres in the UK offered prehabilitation program to their patients compared to 66% for other surgical specialties.³¹ Only one centre offered multimodal prehabilitation as recommended by ERAS (nutrition, exercise, and psychological).³¹ The reluctance in adopting prehabilitation is likely to be multifactorial from financial, logistics, hesitance from clinician due to fear of precipitating an acute event, perceived limited waiting time and inconclusive evidence of improving outcome.

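### The secondary comparison with usual care mixes the programme with patient selection, and the trial ends before the last participant's post-operative outcomes can occur

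*Protocol*

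**What the plan says.** The Abstract gives the design: "This single centre, prospective, pilot feasibility trial will recruit 20 inpatients awaiting cardiac surgery". All eligible patients are offered the programme (Patient recruitment and screening), so there is no concurrent control.

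Three places deal with post-operative outcomes:

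- Outcome measures, secondary objectives: "To identify differences in length of hospital stay, complications and readmission rates to hospital following surgery compared to usual care (based on previously collected data". The source is not named.
- Statistical method, on the same three outcomes: "These can be compared to national data".
- Secondary objective, after listing adverse events, stay, complications and readmission: "This will give us signals for safety concerns and potential efficacy of the program".

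The only local dataset described is the audit in the Abstract and under Setting: "we will be conducting an audit looking into patients who had cardiac surgery in 2022". It draws on a database with wide coverage: "All patients who had cardiac surgery in our department will be entered onto an audit database as routine".

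Entry to the trial is narrower. Setting says: "For the purposes of this pilot, only patients that present directly to CHH and able to communicate in English will be considered". The exclusion criteria remove clinically unstable patients, those with certain diagnoses or functional impairments, those who refuse, and those facing surgery within 72 hours of arrival. Safety adds withdrawal after entry for participants who cannot manage even resistance exercise or cannot perform the test at all.

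Outcome measures also defines the end of the trial as the last participant's day of surgery.

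**The concern.** An objective of finding differences from usual care needs a comparator that stands for what these patients would have experienced without the programme. Neither source is described in a way that makes it one. The two sections do not clearly name the same source, and neither limits it to patients of the kind enrolled. A gap in complications or stay could then appear with no programme effect, or a real effect could be hidden.

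The Protocol itself treats the selection factors as relevant to outcome. The exercise section of the background says that pneumonia incidence runs from 2% to 35% according to population and type of operation. One stated purpose of the audit is to examine "the potential impact of preoperative waiting time on patient outcome such as post-operative complications and post-operative stay".

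At stake is the reading of a secondary result that may inform a larger study. A second, separate problem is that the end-of-trial definition falls before the last participant can have any of the three outcomes.

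**Working it through.** **1. Trial group against the possible comparators**

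| Feature | Trial group | 2022 local audit | National data |
|---|---|---|---|
| Urgency | acute only | all cardiac surgery | no restriction stated |
| Route | direct admission only | no restriction stated | no restriction stated |
| Surgery within 72 h of arrival | excluded if impending | no restriction stated | no restriction stated |
| Stability, language, consent | required | no restriction stated | no restriction stated |
| Withdrawal after entry | possible | no such step | no such step |
| Period | Protocol version dated 06/11/2023 | surgery in 2022 | not stated |
| Centre | single site | same site | other centres as well |

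That the audit is the unnamed source is an inference; the Protocol does not say so.

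**2. Precision with 20 patients**

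The Protocol gives no rate, standard deviation (SD), power or effect size behind the figure of 20, so there is no calculation to reproduce. The 20% rate and the comparator sizes below are assumptions.

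- One group, exact (Clopper-Pearson) 95% intervals: 0/20 gives 0 to 16.8%; 2/20 gives 1.2 to 31.7%; 4/20 gives 5.7 to 43.7%.
- Difference in proportions, 20% in both groups, half-width 1.96 × √[0.2 × 0.8 × (1/20 + 1/N)]: N = 500 gives 17.9 points, N = 100 gives 19.2, N = 50 gives 20.7, N = 20 gives 24.8. A halving from 20% is 10 points, inside all of these.
- Exact test against a rate of 20% treated as known, two-sided 0.05: only 0/20 rejects on the low side (0.8^20 = 0.012). Power for a true 10% is 0.9^20 = 0.12.

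**3. Entry selection, assuming no programme effect**

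Let trial-type patients have a 20% complication rate. Let e be the elective share of the comparator with relative risk RRe, and x the share of acute patients the trial would exclude, with relative risk RRx.

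Comparator rate = 0.20 × [(1 − e − x) + e·RRe + x·RRx]

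Assumed ranges: e from 0 to 0.75, RRe from 0.5 to 0.8, x from 0 to 0.2, RRx from 1.5 to 2.

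- e = 0, x = 0.2, RRx = 2: 0.20 × (0.8 + 0.4) = 24.0%, so trial minus comparator is −4.0 points.
- e = 0.75, RRe = 0.5, x = 0: 0.20 × (0.25 + 0.375) = 12.5%, so trial minus comparator is +7.5 points.

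The sign changes within plausible inputs, so no direction is established.

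**4. Withdrawals, only if they are left out of the count**

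If all 20 starters have a 20% rate and a share w is withdrawn with relative risk RR, the rate in the rest is 0.20 / [1 + w(RR − 1)].

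- w = 1/20, RR = 1.5: 0.20/1.025 = 19.5%.
- w = 5/20, RR = 3: 0.20/1.5 = 13.3%.

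The trial would look 0.5 to 6.7 points better. The Protocol does not say that withdrawn participants are left uncounted, so this shows only why the point should be settled.

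**5. End of trial**

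Post-operative complications, post-operative stay and readmission all arise after surgery. For the last participant the trial is over by definition on the day of surgery. This needs no assumption.

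**The case against.** This is a 20-patient feasibility pilot, and wide intervals are expected. The Secondary objective section speaks of signals, for safety concerns as well as potential efficacy. Statistical method ties potential efficacy to the walk test, grip strength, quality of life and anxiety; for stay, complications and readmission it says only that a comparison can be made. No test, threshold or causal claim is attached to these outcomes, and the Discussion leaves benefit to larger studies. The audit is also meant to look at demographics, comorbidities and mode of presentation, which are close to what a restricted comparator needs. Details such as matching and interval reporting may sit in a statistical analysis plan that is not shown. All of this stands, and it keeps the weight low. It does not remove the stated aim of identifying differences, or the two differing descriptions of the comparator.

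A reader might infer more than the text supports:

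- That entry requires ability to do every element. The exclusion wording is ambiguous, and the Intervention section lets patients who cannot do aerobic exercise do resistance exercise only.
- That outcomes shifted between 2022 and the trial. The Introduction's dated figures (37% operated on within 7 days in 2017/2018, 34% in 2019/2020) precede 2022, and the Discussion's remark on rising waits is general. Calendar time is a possible source of difference, not a demonstrated one.

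On the end date, the Protocol elsewhere commits to collecting these outcomes and mainly the last participants are affected. That shows the intention, but the definition still conflicts with it.

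**Conclusion.** The concern holds, with minor weight. The Protocol sets a comparative aim with 20 patients, no concurrent control, and comparators that are described differently and not limited to trial-type patients. Any difference would combine the programme with selection, and possibly with calendar time. A larger sample would narrow the interval but not remove that mixing.

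It would be tempting to say that the comparison is biased in favour of the programme. The documents do not support that: the entry-selection illustration runs from −4.0 to +7.5 points, and the withdrawal illustration depends on an unstated counting rule. All rates, shares, risk ratios and comparator sizes are assumed. The conclusion rests on the stated populations and does not depend on those inputs.

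The primary feasibility outcome is unaffected. The end-of-trial inconsistency is a separate point that follows from the text alone.

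**What to change.** 1. Reword the objective so that stay, complications and readmission are described alongside usual-care data, and state that differences will not be attributed to the programme.
2. Name one main comparator: the 2022 local audit, restricted as far as its fields allow to acute, directly admitted patients without the listed exclusion diagnoses. Add a 72-hour wait filter and label it approximate, because the trial rule looks forward to impending surgery and Safety allows surgery to be brought forward after entry. Keep national data as context.
3. Report all participants who start, including withdrawn participants who allow follow-up through records, with 95% intervals. State the selection and calendar differences that remain.
4. Reconcile the end-of-trial definition with post-operative data collection, for example by a separate end of data collection.

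The cost is wording plus a filter on data the team already plans to extract, if the fields exist. Some entry rules, such as language, consent and ability to exercise, may not be matchable. The audit description does not mention readmission, so that comparison may be lost and readmission reported for trial patients alone.

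A restricted comparator is smaller. For a mean difference the 95% half-width is 1.96 × √(1/20 + 1/N): 0.45 SD at N = 500, 0.48 at 100, 0.52 at 50 and 0.62 at 20 (assumed sizes). The loss is modest until the cohort nears the trial's own size (0.620/0.447 = 1.39, about 39% wider than at 500). Data collection for the last participants would finish slightly later.

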The concept of prehabilitation whilst not new, has evolved over the years. It has been used to describe preoptimization of medical conditions⁴ to interventions aimed at improving nutritional (N), Exercise capacity (E), and worry reduction (W) to reduce the effect of health deconditioning.⁵ This concept has been adopted by the Society of Enhanced Recovery after Surgery (ERAS). Regardless of the definition, prehabilitation is any intervention that prepares a patient, before an actual stress or physiological insult with the aim of improving their ability to recover. Evidence of the benefits of prehabilitation is well established in cancer and orthopaedic patients. However, evidence amongst cardiac surgery population is lacking. Prehabilitation is slow to develop in this group partly due to the concerns of adverse events amongst those with pre-existing heart condition.

During the COVID-19 pandemic, waiting times for coronary artery bypass graft (CABG) increased by 94%.¹ According to NACSA, it takes an average of 11 days from angiography to surgery for an urgent inpatient coronary artery bypass graft (CABG).¹ Median waiting time ranged from 7 to 24 days.¹ This is in contrast to the national guidelines stating that these operations should be carried out within 7 days.¹ Only 34% of acute patients receive their surgery within 7 days in 2019/2020 compared to 37% in 2017/2018.¹ The delay could be due to a multitude of reasons such as waiting for anti-platelet therapy to wear off, optimisation of medical conditions, lack of beds in tertiary hospitals, or awaiting further investigations. Traditionally, inpatients are told to minimise activity and maintain bed rest. This advice is mainly due to fear that physical activity may worsen the condition or precipitate complications. In some cases, this has led to a phenomenon now known as 'pyjama paralysis' where patients become psychologically bed-bound from not being encouraged to mobilise or retaining independence whilst being in hospital. As a result of prolonged inactivity, patients become deconditioned, leading to extended hospital stays for non-medical reason.

Prehabilitation- Nutrition

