All study participants will be given a booklet containing psychoeducation information. The booklet aims to explain the emotions they may feel whilst being in hospital, symptoms of anxiety, suggest how to manage anxiety, behavioural strategies that may help and signposting if they require further support. In addition to this, the participants will be given access to audio on guided meditation and relaxation. Both the booklet and audio are designed with input from in-house clinical psychologist.

Patients will be asked to score themselves on CAQ and EQ-5D-5L on day 0 and on day 7 or day before surgery. During the second assessment of CAQ and EQ-5D-5L, patients will be asked if they have read or used either the psychoeducation booklet or audio. Hospital staff will be alerted of participants that score highly and considered high risk. In addition, they will be referred to the clinical psychologist or in-hospital psychiatry liaison team.

Additional information collection

All participants will be given a diary. They will be requested to record number of times they performed unsupervised exercise, and for how long. They are also asked to document their food intake. The diary is also used as a mood monitor. Participants are encouraged to write down how they felt, if they used the recommended technique and any benefit they may experience.

Participants will be interviewed for a feedback on the prehabilitation program. The questions will centre around their opinion of the intervention in terms of acceptability, enjoyment, usefulness, accessibility and achievability. We will be gauging their reception to the exercise, psychoeducation booklet as well as mindfulness audio.

Patient and public involvement

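### Improvement from baseline in one uncontrolled group of 20 is read as potential efficacy, although the four measures have no comparator and the protocol's own rationale is deconditioning during the wait

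*Protocol*

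**What the plan says.** The Abstract describes the design: "This single centre, prospective, pilot feasibility trial will recruit 20 inpatients awaiting cardiac surgery". No control group appears anywhere, and the programme is offered to everyone enrolled; on the psychological component, for example, "All study participants will be given a booklet containing psychoeducation information".

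Under Outcome measures, the first secondary objective is "To identify a signal of efficacy for positive changes in physical health exercise, mental wellbeing, and quality of life". The Statistical method section says how that signal will be read: "Improvement in 6MWT, hand grip, EQ-5D-5L and CAQ will indicate potential efficacy of intervention".

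The second secondary objective compares hospital stay, complications and readmissions with usual care from previously collected data, and the Statistical method section mentions national data for the same three. Neither section names a comparator for the walk test, grip, EQ-5D-5L or CAQ.

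On the waiting period, the Introduction says: "As a result of prolonged inactivity, patients become deconditioned, leading to extended hospital stays for non-medical reason". Its list of possible reasons for delay includes "waiting for anti-platelet therapy to wear off, optimisation of medical conditions".

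The Abstract's secondary outcomes include "improvement in 6 minutes walk test (6MWT), hand grip strength, quality of life, anxiety scores and spirometry". Spirometry is also listed under Secondary objective, Baseline data collection and Outcome measures, but not in the efficacy sentence.

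**The concern.** In a single group, change from baseline is the sum of any programme effect, whatever would have happened during the wait anyway, and chance. The efficacy sentence treats an improvement in that sum as pointing to the first part. It names no outside reference and carries no caveat that would separate the parts.

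The protocol's own rationale makes zero change the wrong benchmark. If inactive inpatients lose condition, the natural reference for walking distance and grip lies below baseline. A programme that only prevented the loss would leave these measures flat, and the sentence has no place for that result.

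What is at stake is how a secondary result is reported. An improvement could be published as an efficacy signal when the design cannot support that reading, or a flat result could go unrecognised as compatible with benefit. The feasibility and acceptability results do not depend on it.

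**Working it through.** The protocol gives no power calculation, effect size or SD, so there is no figure to reproduce. The check asks how often the mean change would be favourable under different truths.

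**Inputs from the protocol.** n = 20 (Abstract); four measures named (Statistical method); one group, with no comparator for them.

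**Assumptions, none given in the protocol.**
- A measure counts as improved if its mean change is favourable. Each is coded so that positive is better.
- Mean changes are approximately normal.
- Programme effect *e* and natural drift *d* are in units of the SD of the change.

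**Formula.** P(mean change favourable) = Φ((e + d) × √n), with √20 = 4.472.

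**1. Chance alone.** With e = 0 and d = 0, Φ(0) = 0.50 per measure, at any n. This needs no assumption about drift.

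**2. No effect, upward drift (n = 20).**
- d = 0.2: Φ(0.894) = 0.81
- d = 0.3: Φ(1.342) = 0.91
- d = 0.5: Φ(2.236) = 0.99

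**3. True effect e = 0.3, downward drift (n = 20).**
- d = 0: Φ(1.342) = 0.91
- d = −0.3 (decline exactly prevented): Φ(0) = 0.50
- d = −0.5: Φ(−0.894) = 0.19

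**4. Fewer patients with follow-up data (n = 10).** The pattern is the same. With no effect, drifts of 0.2 and 0.5 give 0.74 and 0.94. With e = 0.3, drifts of 0, −0.3 and −0.5 give 0.83, 0.50 and 0.26.

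**5. Four measures together, no effect and no drift.** All four favourable has probability 0.5⁴ = 0.06 if the measures are independent, 0.20 at pairwise correlation 0.5 and 0.31 at 0.8. At least one favourable has probability 1 − 0.5⁴ = 0.94, 0.80 and 0.69 respectively. Requiring all four guards against chance but much less against a shared drift: if each drifts by +0.3 independently, 0.91⁴ = 0.69. It also makes prevented decline harder to see: at 0.50 per measure, 0.5⁴ = 0.06.

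**The case against.** Several parts of the opposing case are right and limit the point.

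- **Upward drift.** A reader might infer that the protocol itself describes these measures moving both ways during the wait. It states only deconditioning. Medical optimisation is listed as a possible reason for delay, with no statement that any measure improves, and a gain from repeat testing is not mentioned. The exclusions for clinical instability also narrow the room for acute recovery. Upward drift is therefore an inference, though the 0.50 from chance does not rely on it.
- **The converse.** A reader might infer that unchanged values will be reported as no effect. The sentence does not say so; it is silent on stability.
- **Built-in success.** A reader might take 0.94 as the chance of a false signal. That needs any one measure to suffice, whereas the sentence joins the four with *and*. How they are combined, and any minimum size of change, may be settled in a statistical analysis plan that is not shown, so neither counts as a fault here.
- **Consequences.** A reader might fear that a larger study would be wrongly launched or stopped. The Discussion links larger studies to exercise proving possible in this population and leaves proof of benefit to them.
- **Spirometry.** It remains a listed and measured outcome. Its absence from one sentence looks like a slip and does not show that an unfavourable result would be set aside.
- **Hedging.** The wording is cautious (*potential*, *signal*), efficacy is secondary, and a single group is acceptable for a feasibility pilot.

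The core still stands. Cautious words weaken the conclusion but supply no comparator. The inference is written into the protocol, so an analysis plan that follows it inherits the problem.

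**Conclusion.** The point holds as a fault of interpretation in a secondary objective. As written, the plan reads uncontrolled improvement as potential efficacy and does not recognise that stability could be benefit under the protocol's own rationale.

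With no effect and no drift, a measure judged on the sign of its mean change looks improved half the time, however many patients are enrolled. Drift then decides much of the reading. At n = 20, an assumed rise of 0.2 to 0.5 SD of the change gives apparent improvement with probability 0.81 to 0.99 with no effect. An assumed decline of 0.3 to 0.5 SD cuts the chance of seeing an assumed 0.3 SD benefit from 0.91 to between 0.50 and 0.19. These sizes are illustrations. The direction of the downward case comes from the protocol, most directly for walking distance and grip; the upward case is inferred.

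The omission of spirometry is a smaller inconsistency, to be corrected in the same edit. Nothing here touches the primary outcome or calls for a control group in this pilot.

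**What to change.** In the Statistical method section, replace the efficacy sentence with:

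> Within-patient changes in 6MWT, hand grip, spirometry, EQ-5D-5L and CAQ will be reported descriptively with 95% confidence intervals. Without a concurrent control, neither improvement nor lack of change will be attributed to the programme.

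Under Outcome measures, align the first secondary objective: describe the change in these measures, their variability and their completeness, to inform a controlled trial. The parallel mention of potential efficacy under Secondary objective should follow.

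The cost is wording only, with no new patients, visits or data. The downside is that the pilot can no longer claim an efficacy signal from improvement alone.
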